3 OBJECTIVES AND OUTCOME MEASURES/ENDPOINTS

3.1 Objective

The objective of this trial to evaluate the safety and efficacy TaTME for patients with mid and low rectal cancer.

3.2 Primary endpoint/outcome

The primary endpoint is the percentage of patients with local recurrence after 3 years of follow-up.

3.3 Secondary endpoints/outcomes

Pathological

- Involvement of CRM (defined as tumour cells within 1mm from the lateral surface of the mesorectum, centrally reviewed by pathologists)
- Quality of specimen (as proposed and published by Quirke et al.)¹⁴
- Distal resection margin (defined as distance in cm from distal border of the tumour to distal resection surface)
- Translational research will be performed on predictive/prognostic biomarkers and imaging methods.

Clinical

- Length of hospital stay postoperatively (calculated as time from surgery to discharge in days)
- Morbidity within 28 days after surgery and within 90 days (graded by Clavien-Dindo Classification)
- Percentage of sphincter saving procedures (defined as colostomy percentage at 1 year postoperatively)
- Mortality within 28 days after surgery and within 90 days
- Local recurrence at five years (defined as cancer recurrence within the pelvic and perineal area)
- Disease-free survival at three and five years (calculated as time from surgery to last follow-up or date of recurrence)
- Overall survival at three and five years (calculated as time from surgery to last follow-up or death)

Quality of life

- Postoperative health related quality of life (quality adjusted life years) and functional outcome (measured with EORTC QLQ-CR29 and C30, EQ5D and LARS score). A difference of more than 10% in the EORTC list is considered significant.

See 'Chapter 12 Follow-up' for follow-up moments.

Costs (national) (sidestudy)

- In-hospital direct and indirect costs (measured with EQ5D and cost incremental analysis)
- Out-of-hospital postoperative costs (measured with EQ5D and cost incremental analysis)

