The aim is to show non inferiority of TaTME compared to standard laparoscopic TME for mid and low rectal cancer local recurrence after 3 years of follow-up as primary endpoint. Secondary endpoints include morbidity and mortality, residual mesorectum on postoperative MRI, pathology, disease-free and overall survival, percentage of sphincter saving procedures, functional outcome and quality of life.

Statistics and randomisation

This trial is designed as a non-inferiority trial. The expected percentage of patients with a local recurrence after laparoscopic TME surgery is 5% after 3 years. TaTME is believed to be inferior to laparoscopic TME when there is a difference in local recurrence rate of more than 4% after 3 years in favour of conventional TME. Therefore, sample size is calculated based on non-inferiority with a difference of 4% with a one-sided level of significance of 2,5%, a power of 80% and a 5% drop-out rate. A total of 1104 patients is needed, 735 patients in the TaTME arm and 369 patients in the laparoscopic TME arm. Randomisation will be in a 2:1 ratio in favour of the TaTME procedure. It will be stratified for T-stage, preoperative radiotherapy, height of the tumour, gender and BMI. All analyses will be performed on intention-to-treat basis.

Main selection criteria

Patients with a histologically proved single mid or low rectum carcinoma (0-10cm from anal verge) on MRI, eligible for curative TME surgery with a intention for anastomosis, are included. Main exclusion criteria are T4 tumours, T3 tumours with a suspected involved mesorectal fascia (MRF) after neoadjuvant therapy, patients with concomitant metastases or other malignancies, with malignancies in their medical history or with signs of acute mechanical obstruction by the tumour.

Follow-up

Follow-up is based on international guidelines including imaging of the pelvis after three years with extra functional outcome questionnaires. Patients will visit outpatient clinic at least yearly for a follow-up period of five years. At the outpatient clinic the physician will carry out anamnesis and perform physical examination to check for distant metastasis and/or local recurrence. In case of the development of recurrence disease, follow-up should be pursued up to 3 years after diagnosis of recurrence.

Hypothesis

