13.1 Definitions of recurrent disease

Evidence of recurrent disease is accepted when one of the following criteria is present:

- Local macroscopic tumour assessed by colono- or proctoscopy, (PET-)CT-scan or MRI of the pelvis
- Liver metastases on ultrasound, (PET-)CT-scan or MRI
- Lung metastases on chest radiography, (PET-)CT-scan or MRI
- Bone metastases on radiography, (PET-)CT-scan, MRI or bone scintigraphy
- Death with rectal cancer

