14.2 Statistical analysis plan

Baseline numerical data will be described in means, standard deviations or medians and interquartile ranges, baseline categorical data will be displayed in percentages. All comparative analyses will be conducted on an 'intention to treat' basis. Consequently, patients who are randomised to TaTME and converted to a laparoscopic or open TME, will be analysed in the TaTME group. Patients who are randomised to a laparoscopic resection and converted to TaTME or open TME, will be analysed in the laparoscopic group. Ninety days postoperative mortality, pathological resection margin and complication rates will be compared using the Chi-square test or an exact test if necessary. Local recurrence rate, disease-free and overall survival will be compared using the Log-rank test. Exploratory analysis of the prognostic effects of various baseline factors on disease-free survival will be carried out through multivariate Cox-regression. Apart from intention to treat analyses, per protocol analyses will be applied.

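### Disease-free survival as defined censors deaths without rectal cancer, and both survival endpoints start at surgery, so randomised patients who are never operated on have no start date

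*Protocol*

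**What the plan says.** Section 3.3 of the protocol fixes both survival endpoints. DFS reads "Disease-free survival at three and five years (calculated as time from surgery to last follow-up or date of recurrence". The next line reads "Overall survival at three and five years (calculated as time from surgery to last follow-up or death". Death is an end point for OS and is absent from DFS.

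Section 13.1 says what counts as recurrence: "Evidence of recurrent disease is accepted when one of the following criteria is present". The list has local tumour, metastases in liver, lung or bone, and "Death with rectal cancer".

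On the analysis set, the Trial Summary states "All analyses will be performed on intention-to-treat basis", and section 14.2 states "All comparative analyses will be conducted on an 'intention to treat' basis". Section 14.2 explains this by conversion: "Consequently, patients who are randomised to TaTME and converted to a laparoscopic or open TME, will be analysed in the TaTME group". The test is also fixed there: "Local recurrence rate, disease-free and overall survival will be compared using the Log-rank test". DFS is used again in the exploratory Cox model (14.2) and in the subgroup hypothesis on stage (14.3).

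Section 15.6 collects the date and cause of death and, for recurrences, the site without restriction.

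**The concern.** A DFS that does not end at death from any cause is a time to recurrence under another name. A patient who dies without rectal cancer leaves the risk set as if still disease-free and merely no longer observed. The Kaplan-Meier curve then estimates what would happen if nobody died of anything else, and lies above the proportion of patients actually alive and free of disease.

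The trial compares two operations, and deaths around or after surgery are one way in which they could differ. DFS would not show such a difference.

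The words in 13.1 on death are also open to interpretation. Whether an early death after a complete resection is a death with rectal cancer is a judgement, made in a trial that section 4 describes as unblinded.

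Starting the clock at surgery raises a separate question: where do randomised patients belong who never reach surgery?

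**Working it through.** **1. Which deaths count.** Putting 3.3 and 13.1 together:

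| Event | DFS as written | OS as written |
|---|---|---|
| Local, liver, lung or bone recurrence | event | – |
| Distant recurrence elsewhere (e.g. peritoneum, brain) | not listed in 13.1 | – |
| Death with rectal cancer | event, through 13.1 | event |
| Death without rectal cancer | censored at last follow-up | event |
| Death after randomisation, before surgery | no start date | no start date |
| Never operated on | no start date | no start date |

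**2. Size of the DFS overstatement.** The protocol states no DFS, recurrence-of-any-kind or mortality rate, so these inputs are assumptions: R, 3-year recurrence of any kind, 20–30%; D, 3-year death without rectal cancer, 2–10%. The two hazards are taken as independent and constant.

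- As written (such deaths censored): 1 − R
- Deaths counted: (1 − R)(1 − D)
- Overstatement: (1 − R) × D

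| R | D | As written | Deaths counted | Difference (points) |
|---|---|---|---|---|
| 30% | 2% | 70.0% | 68.6% | 1.4 |
| 25% | 2% | 75.0% | 73.5% | 1.5 |
| 25% | 4% | 75.0% | 72.0% | 3.0 |
| 25% | 6% | 75.0% | 70.5% | 4.5 |
| 25% | 10% | 75.0% | 67.5% | 7.5 |
| 20% | 10% | 80.0% | 72.0% | 8.0 |

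The range is 1.4 to 8.0 points.

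**3. Between the arms.** With the same R and D in both arms, both curves are shifted alike. If D differed, the part missed would be (1 − R) times the difference in D. With R = 25% and D of 4% against 6% (hypothetical), DFS would be 72.0% against 70.5%, a gap of 1.5 points, while the definition as written gives 75.0% in both arms.

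**4. Does a start at surgery inflate survival?** Assume a constant hazard beginning at surgery and 75.0% at 3 years from surgery, so h = −ln(0.75)/3 per year. At 3 years from randomisation the value is exp[−h(3 − w/52)] for a wait of w weeks:

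- w = 2: 75.3%
- w = 6: 75.8%
- w = 12: 76.7%

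Counting from surgery gives a slightly lower figure. It could raise the estimate only by leaving out deaths before surgery and patients never operated on. Their number is not given. The whole allowance for drop-out and cross-over in 14.1 is 5%, or 1104 × 0.05 ≈ 55 patients, and this covers more than the unoperated.

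**5. The protocol's own sample size.** Control n = (1.960 + 0.842)² × 0.05 × 0.95 × (1 + 1/2) / 0.04² ≈ 350, so 350 + 700 = 1050. Allowing for 5%: 1050/0.95 ≈ 1105, or 1050 × 1.05 ≈ 1103. The stated 1104 is reproduced. It rests on local recurrence at 3 years only, so redefining DFS and OS does not change it.

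**The case against.** The strongest reply is that a reader might infer from 3.3 that DFS ignores death altogether, and it does not: 13.1 brings in death with rectal cancer. That stands. The gap is confined to the other deaths, and since the phrase is not sharply defined, placing postoperative deaths outside it is the natural reading rather than the only one.

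A reader might also infer that OS is overstated because it starts at surgery. The documents do not support this. OS counts death without qualification, and step 4 shows that the later origin does not in itself raise the figure.

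Nor does the origin overturn intention-to-treat as a whole. Sections 4 and 14.2 use the term for analysis by allocated arm, and a start at surgery moves nobody between arms. The conflict is limited to events before surgery and patients never operated on. The surgery origin also fits the schedule: section 12.1 times pelvic imaging at three years after the operation.

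The trial as a whole does not lose deaths. Mortality within 28 and 90 days is a separate secondary endpoint, 90-day mortality has its own test in 14.2, and OS counts every death after surgery.

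On sites, 13.1 does not say that only the listed sites qualify, and 15.6 records any site. This is a point of clarity, with no number attached.

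Finally, a statistical analysis plan might settle the details. For unoperated patients that is partly fair. For DFS it is not: the protocol does not leave the definition open but states one, and a later plan that counted all deaths would depart from it.

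**Conclusion.** The concern holds for DFS. Followed as written, sections 3.3 and 13.1 censor deaths without rectal cancer and overstate 3-year DFS, by about 1.4 to 8 points if R is 20–30% and D is 2–10%. These rates are assumed and the hazards are taken as independent. The direction does not depend on the values; the size does.

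This is an error in the level of the curve. A distorted comparison between the arms would need deaths without rectal cancer to differ by arm, and nothing in the protocol shows that they would.

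For both endpoints, a randomised patient with no operation has no time origin, so the analysis set falls short of the intention-to-treat set by a number that cannot be derived from the document. The site list in 13.1 needs clarifying.

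The matter should be corrected before analysis but does not threaten the trial's main conclusion. DFS and OS are secondary endpoints that do not enter the sample-size calculation, and the primary endpoint, the margin and the 1104 are untouched.

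**What to change.** - **DFS:** define it as time from randomisation to the first of local recurrence, distant recurrence at any site, or death from any cause.
- **OS:** define it as time from randomisation to death from any cause.
- **Analysis set:** include all randomised patients in both, and say how those without surgery are handled.
- **Section 13.1:** replace the three named organs with any distant metastasis.
- **If the present quantity is wanted:** call it time to recurrence and treat death as a competing event.
- **Sensitivity analysis:** a surgery origin may be kept for this purpose.

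The cost is an amendment of wording. Date and cause of death and site of recurrence are already collected under 15.6, and the date of randomisation is known. No extra patients or visits are needed.

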14 STATISTICS AND DATA ANALYSIS

14.1 Sample size calculation

The primary endpoint is the local recurrence after 3 years. In laparoscopic TME the percentage of local recurrence is estimated 5%. A local recurrence increase of 4% is believed to be inferior. Based on this difference, sample size calculation has been done with a one-sided level of significance of 2,5% and a power of 80%. A total of 1104 patients is needed, 735 patients in the TaTME arm and 369 patients in the laparoscopic TME arm.

In this sample size calculation, additional postrandomisation analyses (drop-out, cross-over total 5%), is taken into account.

Randomisation will be stratified for

- T3a and less / T3b and more
- Downstaged with chemoradiotherapy: yes / no / NA
- Preoperative radiotherapy: yes / no
- Height of the tumour: 0-2.0cm / 2.1-5.0cm / 5.1-10cm
- Gender: male / female
- BMI \leq 30.0 / BMI $>$ 30.0

The randomisation will be executed in such a way that concealment of allocation for the indicating surgeon is guaranteed.

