15.6 Data collected during follow-up period

Once a year the following data will be collected:

- Date of visit
- Adjuvant therapy
- Reversion of ileostomy
- Details on recurrence, including date and method of diagnosis, site of recurrence and treatment consequences
- Details on complications
- Date and cause of death

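### Disease-free survival is defined without death as an event, so it is time to recurrence with most recurrence-free deaths censored, and the percentage is overstated

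*Protocol*

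**What the plan says.** Section 3.3 lists disease-free and overall survival as neighbouring clinical endpoints, each with its own formula. The first reads "Disease-free survival at three and five years (calculated as time from surgery to last follow-up or date of recurrence", which leaves recurrence as its only event. The formula in the bullet that follows it does name death: "Overall survival at three and five years (calculated as time from surgery to last follow-up or death". Section 13.1, which lists what is accepted as evidence of recurrent disease, ends with "Death with rectal cancer".

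Section 14.2 gives the analysis: "Local recurrence rate, disease-free and overall survival will be compared using the Log-rank test". It also plans an exploratory Cox model of baseline prognostic factors with this endpoint as the outcome. It gives no other event definition for disease-free survival and mentions no competing risk. Section 14.3 uses disease-free survival in the subgroup hypothesis by stage.

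Mortality also appears separately. Section 3.3 lists "Mortality within 28 days after surgery and within 90 days", section 14.2 plans a test of 90-day mortality, and section 15.6 collects "Date and cause of death" every year.

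**The concern.** Disease-free survival is normally read as the proportion of patients who are alive and free of disease. Under the formula in 3.3, a patient who dies without recurrence, for example of sepsis or cardiac disease, does not count as a failure. That patient leaves the analysis at last follow-up as if still at risk of a later recurrence.

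Three things follow:

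- The percentage reported at three and five years is too high for the name that it carries.
- A difference between the arms in recurrence-free deaths contributes nothing to this comparison.
- The clause in 13.1 brings in some deaths through the definition of recurrence, and its boundary is unclear. A death soon after a curative resection could be read as a death with rectal cancer (an event) or as a death without recurrence (censored). Allocation is open (section 4), and the protocol describes no rule for deciding.

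**Working it through.** **The plan's own figure.** The protocol gives no rate, event count or power for disease-free survival. The only figure to reproduce is the primary-endpoint sample size, for which "sample size calculation has been done with a one-sided level of significance of 2,5% and a power of 80" percent applies, with 5% local recurrence in both arms, a margin of 4 points, 2:1 allocation and 5% drop-out (14.1 and the trial summary).

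- Control arm: 0.05 × 0.95 × 1.5 × (1.960 + 0.842)² / 0.04² = 349.5
- After drop-out: 349.5 / 0.95 = 367.9 control, 735.8 TaTME, 1103.7 in total
- Stated: 369, 735 and 1104

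The figure reproduces to within rounding and does not involve disease-free survival, so nothing below changes it.

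**Direction.** Take one data set and turn some censored deaths into events. The Kaplan-Meier curve can then only stay the same or fall. The direction of the overstatement needs no assumption about rates.

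**Size, simple version.** All rates are assumed. Let R be the probability of recurrence and D the probability of death without recurrence, taken as independent.

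- As defined: 1 − R
- With any death an event: (1 − R) × (1 − D)
- Overstatement: (1 − R) × D

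| Time | R | D | As defined | Death counted | Overstatement (points) |
|---|---|---|---|---|---|
| 3 years | 25% | 2% | 75.0% | 73.5% | 1.5 |
| 3 years | 25% | 5% | 75.0% | 71.3% | 3.8 |
| 3 years | 25% | 8% | 75.0% | 69.0% | 6.0 |
| 5 years | 30% | 5% | 70.0% | 66.5% | 3.5 |
| 5 years | 30% | 9% | 70.0% | 63.7% | 6.3 |
| 5 years | 30% | 14% | 70.0% | 60.2% | 9.8 |

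**Size, second model.** Assume constant hazards plus operative mortality m at time zero. The value as defined is exp(−h_rec × T). With death counted it is (1 − m) × exp(−(h_rec + h_death) × T). With 3-year recurrence of 15% to 25%, m of 1% to 3% and other recurrence-free deaths of 2% to 6% at 3 years, the overstatement is 2.2 to 7.5 points at 3 years and 2.6 to 9.5 points at 5 years. In the central case (20%, 2%, 4%) the 3-year values are 80.0% against 0.98 × 0.80 × 0.96 = 75.3%. The 5-year values are 68.9% against 63.1%.

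**What the clause in 13.1 does.** In the central case, if operative deaths were read into the clause and other recurrence-free deaths were not, the 3-year value would be 0.98 × 0.80 = 78.4%. If every death were read into it, the value would be 75.3%; if no recurrence-free death were, 80.0%. The protocol does not say which reading applies.

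**Effect on the comparison.** Let the arms differ only in operative mortality, 3% against 1%, with the central rates otherwise.

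- As defined: 80.0% in both arms, a difference of 0.0 points
- Death counted: 0.97 × 0.80 × 0.96 = 74.5% against 0.99 × 0.80 × 0.96 = 76.0%, a difference of 1.5 points

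**The case against.** Several arguments limit the point, and most of them stand.

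- **Event and censoring rules often sit in the analysis plan, and 3.3 never uses the word censored.** This stands in part. But the protocol does not leave the endpoint open. It states a formula, that formula omits death, and the next bullet includes it. An analysis plan that counted death would contradict 3.3, and one that followed 3.3 would carry the omission forward.
- **Some deaths do count.** This is correct. A reader might infer that the endpoint ignores every death, but 13.1 rules that out. What remains is that other recurrence-free deaths are not events and that the clause has no clear edge.
- **The trial measures operative mortality elsewhere.** This is correct. A reader might infer that the trial cannot see surgical deaths. The 28- and 90-day mortality and overall survival endpoints, serious adverse event reporting (16.2.2) and the safety board's review (16.3) show otherwise. Direct comparison is also the sharper tool. With 735 and 369 patients, 3% against 1% mortality has a standard error of √(0.03 × 0.97/735 + 0.01 × 0.99/369) = 0.8 points, so the 2-point difference is about 2.5 standard errors. The 1.5-point difference in disease-free survival has a standard error of √(0.75 × 0.25/735 + 0.75 × 0.25/369) = 2.8 points, so it is only about half of one.
- **Informative censoring is not shown.** This is correct. A reader might infer it, but the calculations assume independence, under which censoring is not informative. They show only the gap between a composite and one of its components.
- **The rates are assumed, and the level shift affects both arms.** This is correct. The endpoint is also secondary and unpowered, the Cox model is labelled exploratory, and the stage hypothesis in 14.3 compares stages within each arm rather than treatments.

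**Conclusion.** The point holds as a defect in the definition of one secondary endpoint. Under 3.3, disease-free survival is time to recurrence with recurrence-free deaths censored, apart from those taken in by the ambiguous clause in 13.1. It overstates disease-free survival by about 1.5 to 6 points at 3 years if recurrence is 25% and recurrence-free deaths are 2% to 8%. The second model gives a similar range. The direction follows from the definition; the size rests entirely on assumed rates and on independence of death and recurrence. If the clause in 13.1 were read to cover more deaths, the overstatement would shrink.

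A difference between the arms in deaths that are not counted is kept out of this endpoint, but not out of the trial. The primary endpoint and the sample size are not affected.

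**What to change.** In 3.3, take one of two routes:

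1. Define disease-free survival as the time from surgery to the first of local recurrence, distant recurrence or death from any cause. Censor only patients who are alive and recurrence-free, at their last follow-up.
2. Keep the present quantity, rename it time to recurrence, and analyse it with death as a competing event.

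The first matches the endpoint's name and the log-rank and Cox analyses in 14.2.

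Also state how the clause on death with rectal cancer in 13.1 relates to the chosen definition, including for early postoperative deaths. It need not be deleted. Under the first route every death is an event whichever way it is classed, and removing the clause could lose recurrences that were never otherwise documented. Under the second route its meaning matters more, because it moves patients between recurrence and the competing event.

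The cost is a few lines of wording. Date and cause of death are already collected (15.6), so no new data are needed. Under the first route the reported percentages become slightly less favourable. The change should be made before disease-free survival is compared between the arms, because in an open trial a later choice of event definition would invite doubt.

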4 TRIAL DESIGN

The study is an international, randomised, non-inferior, multicentre trial comparing traditional and transanal laparoscopic TME as the surgical treatment for rectal cancer. Patients will be accrued by all participating hospitals participating in the COLOR III study group (list of participating hospitals can be obtained through rectalcancersurgery.eu → 'COLOR III Trial'). All centres will follow a quality assurance program of the procedure itself and the data before data will be entered in the COLOR III trial. The COLOR III study group is an international group of surgeons with interest and expertise in minimally invasive colorectal surgery.

The first COLOR study started in 1997 and completed a large RCT in 2003 comparing laparoscopic to open surgery for colon cancer.^{36,37} Hereafter, many centres of this study group joined the COLOR II study group. The COLOR II study group recently completed a major RCT comparing laparoscopic to open TME in the treatment of rectal cancer.

The design involves allocation of all appropriate consecutive patients with mid or low rectum carcinoma to either of the two procedures at a randomisation ratio of 2:1 in favour of the TaTME procedure. Once eligibility has been established and patient details have been noted, the patient will be allocated to either transanal or laparoscopic TME. Assignment to one the two treatment groups will not be blinded. Randomisation will be performed by computer and will be balanced by T-stage, preoperative radiotherapy, height of the tumour, BMI and gender. Data will be analysed on 'intention to treat' basis in case patients are not subjected to the randomised treatment modality. Randomisation will be done through internet: rectalcancersurgery.eu (click 'COLOR III Trial → Professionals').

Included surgical procedures to obtain TME are 1. low anterior resection (LAR) with colorectal anastomosis 2. LAR with coloanal anastomosis

Excluded surgical procedures are extralevator abdominoperineal excision (ELAP) (i.e. patients with tumour in growth (more than 1/3) in the anal sphincter complex or levator ani.

Exclusion criteria are T4 tumours, T3 tumours with a suspected involved CRM after neoadjuvant therapy, patients with concomitant metastases or other malignancies, with malignancies in their medical history or with signs of acute mechanical obstruction by the tumour.

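### Overall and disease-free survival are timed from surgery although all comparisons are declared intention-to-treat, so randomised patients without an operation, or with an event before it, have no valid survival time

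*Protocol*

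**What the plan says.** Section 3.3 (Clinical) fixes the time origin of both survival endpoints:

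- "Overall survival at three and five years (calculated as time from surgery to last follow-up or death"
- "Disease-free survival at three and five years (calculated as time from surgery to last follow-up or date of recurrence"

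Section 14.2 compares both endpoints by log-rank test and states the analysis population: "All comparative analyses will be conducted on an 'intention to treat' basis". The trial summary (Statistics and randomisation) says the same of all analyses. Section 14.2 adds per-protocol analyses as a separate set.

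The protocol also shows what it had in mind under intention-to-treat. Section 4: "Data will be analysed on 'intention to treat' basis in case patients are not subjected to the randomised treatment modality". Section 14.2: "Consequently, patients who are randomised to TaTME and converted to a laparoscopic or open TME, will be analysed in the TaTME group", with a matching rule for the laparoscopic arm.

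On timing, section 4 says: "Once eligibility has been established and patient details have been noted, the patient will be allocated to either transanal or laparoscopic TME". Allocation is not blinded.

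**The concern.** Surgery happens after randomisation. If the survival clock starts at surgery, having been operated on becomes a condition for entering the comparison, and that condition is met or missed after the allocation is known to patient and surgeon. An intention-to-treat comparison should not depend on such a condition.

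Two groups are affected: patients who are randomised but never operated on (withdrawal, progression, loss of fitness, death), and patients who die or progress before the operation. What is at stake is whether the survival comparison keeps the protection of randomisation for everyone allocated, and whether absolute survival is reported for the randomised cohort or for a subset of it.

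**Working it through.** **1. The plan's own figure.** The survival endpoints carry no sample-size figure. The only one is for the primary endpoint, in 14.1: 5% local recurrence in both arms, margin 4 percentage points, one-sided 2.5%, power 80%, allocation 2:1, 5% loss.

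- Control arm: (1.960 + 0.842)² × 0.05 × 0.95 × (1 + 1/2) / 0.04² = 349.5
- Total: 3 × 349.5 = 1048.6
- With 5% loss: 1048.6 / 0.95 = 1103.7, that is 1104, as stated

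This figure does not depend on the origin of overall or disease-free survival, so the change proposed here leaves it alone.

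**2. The order of events.** Section 4 allocates patients once eligibility is established. Section 15.2 collects the type of planned surgery at randomisation; the date of surgery appears only in section 15.4, among the data collected during the operation. Randomisation therefore comes first.

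**3. Applying the definition.** Let R be the date of randomisation, S the date of surgery and E the date of the event or last follow-up. Section 3.3 defines T = E − S.

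| Patient | S | T under 3.3 | Can enter the log-rank test? |
|---|---|---|---|
| Operated, by either technique or converted | exists | E − S ≥ 0 | yes |
| Operated, progression between R and S | exists | E − S < 0 | not with that event |
| Dies between R and S | none | undefined | no |
| Never operated on, alive | none | undefined | no |

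With T = E − R, every row has a non-negative time.

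**4. Does the intention-to-treat wording settle the last three rows?** The rules in 14.2 are about conversions, so they concern operated patients. The wording in section 4, on patients who do not get the allocated modality, can be read to keep non-operated patients in their arm, but 3.3 then gives them no survival time. Because per-protocol analyses are listed separately, an operated-only set is hard to read as the intended meaning of intention-to-treat. No section starts either endpoint at randomisation.

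**5. Size.** The protocol gives no rate of non-operation and no interval from randomisation to surgery. The shares below are assumptions. The last row is an outer bound that treats the whole 5% allowance in 14.1 (drop-out and cross-over together) as non-operation.

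| Share not operated on | Of 1104 | Of 735 (TaTME) | Of 369 (laparoscopic) |
|---|---|---|---|
| 1% | 11 | 7 | 4 |
| 3% | 33 | 22 | 11 |
| 5% | 55 | 37 | 18 |

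The arm columns apply the same share to both arms, because nothing in the protocol suggests otherwise.

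**The case against.** The strongest reply is that the protocol uses intention-to-treat in a narrower sense: analyse by allocated arm whatever operation was done. For patients who had an operation, timing from surgery is compatible with that. The protocol nowhere says that non-operated patients are excluded, and their handling is often settled in a SAP, which is not at hand here. The first part stands: the conflict is confined to patients with no operation or an event before it, and exclusion is a consequence of the definition, not a stated rule. The SAP argument does not remove the point, because the protocol fixes the origin itself; this is a stated rule and not a detail left open.

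The numbers are also likely to be small. T-stage and margin eligibility are judged after (chemo)radiotherapy where it is given (5.2), which suggests a short gap to surgery, and patients must be suitable for elective laparoscopic resection (5.1). This stands.

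A reader might infer more than the documents support:

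- *That waiting time or non-operation differs by arm because the arms need different teams.* Section 4 requires each centre to have at least two surgeons who perform both procedures independently, and says both are already done regularly in the included hospitals. No difference is documented.
- *That the patients left out are those with the worst prognosis.* Some may be, but section 17.1 lets patients withdraw without giving reasons, and they need not do badly.
- *That a material fraction of all deaths is lost.* This needs the mortality of non-operated patients and the overall three-year mortality. The protocol gives neither, and a pooled count would say nothing about the contrast between arms.

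**Conclusion.** The point holds for overall and disease-free survival. Section 3.3 and the intention-to-treat statements in 14.2 and the trial summary cannot both be applied to a randomised patient who is never operated on or who has an event before surgery. As defined, the comparison is one of operated patients.

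The size is modest: 11–33 of 1104 patients if 1–3% are not operated on, which is an assumption, and probably few if the gap to surgery is as short as the staging rule suggests. Both are secondary endpoints; the sample size is unaffected. It would go too far to say that the survival comparison is biased between arms. The protocol leaves that possibility open but contains no evidence for it. The change is worth making because the contradiction exists at any rate of non-operation and is cheap to remove.

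**What to change.** In section 3.3:

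- **Overall survival:** time from randomisation to death from any cause or last follow-up, in all randomised patients, by allocated arm, whether or not operated on.
- **Disease-free survival:** the same origin and population, with two additions. First, an event rule for patients never resected: 3.3 names recurrence as the event, and the criterion of local macroscopic tumour in 13.1, read literally, would be met by an unresected patient from the outset. Second, an analysis window at three years: section 12.1 times the pelvic scan three years after surgery, so it falls later than 36 months after randomisation by the length of the wait, and a recurrence first seen on it would otherwise miss the three-year estimate.
- **Sensitivity analysis:** both endpoints timed from surgery in operated patients. Hospital stay and postoperative morbidity and mortality stay timed from surgery.

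If the sponsor prefers surgery as the main origin, the population should be named as randomised and operated, and not called intention-to-treat.

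The cost is the event rule, the window, and survival follow-up of the few patients not operated on. Yearly follow-up for five years (12.1) and yearly collection of recurrence details and date of death (15.6) are already planned for participants. The list of data collected at randomisation (15.2) does not include the randomisation date; the web system should hold it, but this needs to be confirmed.
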